2.1.2. Secondary endpoints

- **Definition**

Secondary endpoints are as follows:

- Incidence rate of HCV reinfections during both the run-in (i.e., M0 and M6) and intervention period (i.e., M12, M18, M24), both self-reported and laboratory-confirmed, defined as the number of cases divided by the total person-years of follow-up at risk for reinfection
- Incidence rate of any STI during the run-in and intervention period, both self-reported and laboratory-confirmed, defined as the number of chlamydia, gonorrhoea, genital herpes and/or syphilis infections divided by the total person-years of follow-up
- Other HCV-related risk behaviour during run-in versus intervention period, more specifically:
 - Changes in the mean or median number of sex partners (depending on the distribution of the variable of interest)
 - Changes in the mean or median number of condomless anal sex acts with casual partners (depending on the distribution of the variable of interest)
 - Changes in the proportion of participants reporting any individual behaviours that are included in the HCV-MOSAIC risk score
 - Changes in mean or median sexual wellbeing score (depending on the distribution of the variable of interest)
- The proportion of participants achieving an HCV-MOSAIC risk score ≥ 2.0 at the end of follow-up compared between intervention arms (in both ITT and PP populations)

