1.2. TRIAL DESIGN

1.2.1. Study design and methods

This study is an international, multi-centre, phase 2, 3-arm, randomized trial (RT) comparing run-in and intervention periods to evaluate the effect of an online behavioural intervention, a home-based sampling for testing intervention, or both on self-reported behaviours associated with HCV acquisition. The first 6 months of the trial includes follow-up with no intervention (termed the “run-in” period) during which participants receive standard care. At month (M) 6, participants are randomly assigned, with an allocation ratio of 1:1:1, to one of the following three arms: (1) a targeted, online behavioural intervention; (2) a participant-initiated, home-based HCV-RNA self-sampling test service using dried blood spots (DBS); (3) consists of a combination of intervention I and II. Participants continue the intervention for 18 months (termed the “intervention” period) in addition to standard care. During both the run-in and intervention periods, five online questionnaires measuring risk behaviour over the past 6 months are administered (i.e., at M0, M6, M12, M18 and M24 of the study).

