Changes are described for HCV related risk behaviour and sexual wellbeing (see paragraphs 3.5.3 and 3.5.4) during run-in (i.e., M0 and M6) versus intervention period (i.e., M12, M18, M24). We use logistic (for binary outcomes) and linear (for continuous outcomes) regression models, corrected for repeated measurements within individuals using a random-intercept for participant. The relative changes in each endpoint are compared between run-in and intervention periods. These models are run on both the overall study population and stratified by treatment arm (using the same model configuration of fixed-effect covariates as in the primary endpoint).

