2.3. CALCULATION CONVENTIONS

2.3.1. Convention for defining follow-up time

- Follow-up during the run-period is defined as the amount of participation time for each participant enrolled from moment of inclusion (following sign inform consent) until the moment of randomisation
- Follow-up during the intervention period is defined as the amount of participation time for each participant enrolled from moment of randomisation until last study visit

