3.3.2. Clinical characteristics at enrolment (M0) and during follow-up (M6 to M24)

- HCV-related clinical characteristics
 - Previous HCV infections (in counts)
 - Previous HCV treatment (yes/no)
 - HCV genotype
 - Time since first anti-HCV positive test (in years)
- HIV or pre-exposure prophylaxis (PrEP)-related clinical characteristics
 - HIV-status (positive or negative)
 - PrEP-use (yes/no)
 - Type of PrEP regimen (daily or event-driven)
- STI testing and testing outcomes (positive or negative), including chlamydia, gonorrhoea, genital herpes and/or syphilis (self-reported)

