3.4. PRIMARY ENDPOINT

3.4.1. Main analysis

- **Definition**

The proportion of participants achieving an HCV-MOSAIC risk score ≥ 2.0 compared between the run-in (i.e., M0 to M6) and intervention periods (i.e., M12 to M24). ORs are calculated along with their 95%CI in the ITT and PP population as described in paragraph 2.1.1.

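### The SAP's run-in label for the HCV reinfection rate takes in the M0 questionnaire, which reports pre-inclusion events, while run-in person-time starts at inclusion; no rule keeps M0 reports out of the reinfection or STI rates

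*SAP*

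**What the plan says.** - **Reinfection numerator.** SAP 2.1.2 defines the endpoint as "Incidence rate of HCV reinfections during both the run-in (i.e., M0 and M6) and intervention period (i.e., M12, M18, M24), both self-reported" and laboratory-confirmed, with cases divided by person-years at risk.
- **STI numerator.** The next bullet reads "Incidence rate of any STI during the run-in and intervention period, both self-reported and laboratory-confirmed". It names no questionnaires.
- **Denominator.** SAP 2.3.1 counts run-in follow-up "from moment of inclusion (following sign inform consent) until the moment of randomisation", and intervention follow-up from randomisation to the last visit. SAP 2.3.2 also starts HCV time at risk at inclusion. It dates a reinfection midway between the last negative and first positive RNA test.
- **Look-back.** SAP 1.2.1 has "five online questionnaires measuring risk behaviour over the past 6 months are administered (i.e., at M0, M6, M12, M18 and M24 of the study". Protocol 7.3 sends the M0 questionnaire after enrolment.
- **Run-in label elsewhere.** For risk behaviour and wellbeing, SAP 2.2.2 writes "during run-in (i.e., M0 and M6) versus intervention period (i.e., M12, M18, M24", and it gives M0 and M6 as the run-in for the primary endpoint as well. SAP 3.4.1 writes "run-in (i.e., M0 to M6) and intervention periods (i.e., M12 to M24". Protocol 9.1 used month 6 alone as the run-in for the primary outcome.
- **M0 STI data.** SAP 3.3.2 lists "STI testing and testing outcomes (positive or negative), including chlamydia, gonorrhoea, genital herpes and/or syphilis (self-reported" among characteristics recorded at enrolment and during follow-up.

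Neither document says that M0 reports are left out of the incidence rates.

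**The concern.** A rate needs events and person-time from the same window. What a participant reports at M0 happened, apart from any delay in completing the form, before he was included. If those reports count as run-in events, the run-in numerator covers up to about 12 months and its denominator about 6. The intervention period has no such mismatch, because M12, M18 and M24 together look back over exactly its 18 months.

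The error has one direction. It raises the run-in rate, so every arm appears to improve, and a larger sample only makes the false fall more precise. With no untreated control arm (Protocol 3), run-in versus intervention is the planned within-arm evidence on both incidence endpoints. Trial outcomes also feed the transmission model (Protocol 9.5).

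**Working it through.** The documents give no STI rate, expected event count or power for these endpoints, so there is no stated figure to reproduce.

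**1. Are M0 and M6 questionnaires or interval limits?** As interval limits, the matching intervention labels (M12, M18, M24, or M12 to M24 in SAP 3.4.1) would omit the 6 months after randomisation, against SAP 2.3.1. As questionnaires with a 6-month look-back, M12, M18 and M24 cover the intervention period exactly. On the same reading M6 alone covers the run-in, and M0 lies before it. The label therefore conflicts with the person-time rule.

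**2. Size of the mismatch under a constant rate.** Inputs: run-in 0.5 year and intervention 1.5 years (SAP 1.2.1); 78 per arm, 234 in total (SAP 1.4). Let L be the true rate and s the share of the M0 look-back that enters the numerator.

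- Run-in rate = N × L × (0.5 + 0.5s) / (N × 0.5) = L(1 + s)
- Intervention rate = N × L × 1.5 / (N × 1.5) = L
- Rate ratio with no true change = 1 / (1 + s)

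| s | Run-in inflation | Rate ratio with no true change |
|---|---|---|
| 0 | 1.00 | 1.00 |
| 0.25 | 1.25 | 0.80 |
| 0.5 | 1.50 | 0.67 |
| 1 | 2.00 | 0.50 |

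The ratio does not depend on L.

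**3. STI illustration.** The rate is an assumption: 0.2 to 1.0 per person-year, constant over time. At 0.5 per person-year, N = 234 and s = 1:

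- Run-in: 234 × 0.5 × 0.5 × 2 = 117 events in 117 person-years, or 1.0 per person-year (58.5 events if counted correctly).
- Intervention: 234 × 1.5 × 0.5 = 175.5 events in 351 person-years, or 0.5 per person-year.

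The chance of a result significant at two-sided 0.05 with no true change was simulated with 200,000 pairs of independent Poisson counts and a Wald test of the log rate ratio. Per arm (n = 78) at s = 1 it is 55% at 0.2 per person-year, 90% at 0.5 and over 99% at 1.0. With s = 0 it is 4% to 5%. At 0.5 per person-year with partial counting, the normal approximation gives 43% at s = 0.5 and 15% at s = 0.25.

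**4. HCV.** Two illustrative rates follow from Protocol 1.3:

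- Ten times 3.3 per 1,000 person-years = 0.033 per person-year.
- One third reinfected within 2 years: −ln(2/3)/2 = 0.203 per person-year.

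Over 234 × 0.5 = 117 run-in person-years these give 3.9 and 23.7 true events. Each pre-inclusion episode wrongly counted raises the run-in rate by 1/3.9 = 26% or 1/23.7 = 4%. The number of such episodes cannot be derived, because the documents do not say how many participants were cured or cleared in the 6 months before inclusion.

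**The case against.** The strongest reply is that the SAP nowhere instructs anyone to count M0 reports as incident events. Several parts stand.

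- **Run-in means post-inclusion time.** SAP 1.2.1 and 2.3.1 define it that way, and SAP 2.2.2 calculates incidence within the two periods. This shows what was probably intended, but it does not remove the M0 label or the absence of an exclusion.
- **The label is on the HCV bullet only.** In SAP 2.2.2 the M0/M6 wording attaches to proportions, means and scores, where M0 creates no denominator problem. The headings of SAP 3.3 and 3.3.2 separate enrolment (M0) from follow-up (M6 to M24), which suggests that M0 STI results are baseline data. So extending the label to STI is an inference. It is a reasonable one: M0 and M6 are the only run-in questionnaires named in 2.2.2, the incidence models borrow the primary endpoint's fixed-effect configuration, and STI events have no dating rule.
- **HCV has safeguards.** Entry requires negative RNA and no current infection or treatment. Under the midpoint rule, an event dated before inclusion has no valid time at risk. That leaves mainly self-reports without RNA dates, for which the SAP gives no rule. A man recently cured could report at M0 the very infection that made him eligible.

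A reader might infer that the SAP definitely counts M0 events and so builds in a halving of both rates. The documents do not support that. For STI the halving is conditional on the inference above and on counting the whole look-back; for HCV the dating rule, where applied, removes the event.

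**Conclusion.** The concern holds as an inconsistency in the SAP, not as a demonstrated bias of known size. The run-in label for the reinfection rate, the 6-month look-back and the start of person-time cannot all stand, and the literal reading favours the interventions.

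- **HCV:** the direction is clear, but the size is not fixed by the documents. It is limited to resolved infections that escape the dating rule. With few events expected, a handful would matter.
- **STI:** conditional on applying the M0/M6 run-in used elsewhere in the SAP. With a constant rate, inflation is up to 2-fold and the rate ratio with no true change is 0.50 if all M0 reports count, or 0.67 to 0.80 if half to a quarter of the look-back counts. The significance figures also rest on assumed rates and independent Poisson counts.
- **Primary endpoint:** a proportion per questionnaire with no person-time, so this mismatch does not affect it.

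This should be fixed before analysis. It concerns secondary endpoints only.

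**What to change.** In SAP 2.1.2 and 2.2.2:

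- Limit run-in numerators for HCV reinfection and STI to events dated after inclusion and up to randomisation, taken from the M6 questionnaire and laboratory results in that window.
- State that M0 reports of STI and HCV are baseline characteristics only. A self-reported HCV infection should count only if it can be dated after inclusion.
- If the sponsor prefers to keep M0 STI reports in the run-in rate, add the matching 6 months of pre-inclusion person-time for each M0 respondent. This option is not suitable for HCV, where a past infection is a condition of entry.

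Under a constant rate, either STI option returns the rate ratio with no true change to 1.00.

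The cost is SAP wording only, with no new data. Dropping M0 loses some precision compared with keeping M0 STI reports on matched person-time. At an assumed 0.5 per person-year and 78 per arm, the standard error of the log rate ratio is √(1/19.5 + 1/58.5) = 0.26, against √(1/39 + 1/58.5) = 0.21.

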2.2. STATISTICAL METHODS

2.2.1. Descriptive analysis

Descriptive statistical analyses are performed to describe study population characteristics at inclusion, intervention-related outcomes at M12 (i.e., 6 months after randomisation) and at the end of follow-up (e.g., use of services, acceptability and usability) and the number of tests, home-based or otherwise, performed during the intervention period.

- Descriptive analysis is performed overall and per intervention group
- Frequencies of missing data are described for each variable
- Quantitative variables are described in terms of frequency, average, standard deviation, median, minimum, maximum and interquartile range. They can also be presented in class (e.g., age groups) and described in the form of categorical variables, based on medians and quartiles
- Additional descriptive analyses not mentioned in this document might be added to the statistical report

2.2.2. Comparative analysis

The primary endpoint is compared between the run-in period (i.e., at M0, M6) and at each time point during the intervention period (i.e., at M12, M18, M24) using a mixed-effect logistic regression model. In this model, each individual serves as their own control and between-individual differences at baseline are accounted for using a random-intercept. Odd ratios (OR) comparing the odds of run-in versus intervention time points, along with their 95% confidence intervals (CI), are estimated and stratified on study arm. These stratified analysis are performed by including an interaction term between arm and study time point (along with their individual covariate) in the model, while study time points are statistically tested within strata of the study arms. Comparisons between run-in and intervention time points are systematically conducted as follows:

- Unadjusted;
- Adjusted on the randomisation strata (country and, if sufficient numbers of individuals in each intervention arm are available, inclusion centre [3]);
- Adjusted on covariates that could potentially affect the evaluation of the primary outcome

Incidence rates of HCV reinfections and STIs are calculated during the run-in and interventions periods, separately. Considering that few HCV reinfections are likely to occur,

we intend to analyse the relative difference in incidence rates between periods using a Bayesian exponential survival regression model with non to weakly informative *a priori* distributions [4, 5]. The relative difference in incidence rates of STIs are compared between periods using a Poisson regression model with ln of person years of observation as an offset. These models are run on both the overall study population and stratified by treatment arm (using the same model configuration of fixed-effect covariates as in the primary endpoint).

Changes are described for HCV related risk behaviour and sexual wellbeing (see paragraphs 3.5.3 and 3.5.4) during run-in (i.e., M0 and M6) versus intervention period (i.e., M12, M18, M24). We use logistic (for binary outcomes) and linear (for continuous outcomes) regression models, corrected for repeated measurements within individuals using a random-intercept for participant. The relative changes in each endpoint are compared between run-in and intervention periods. These models are run on both the overall study population and stratified by treatment arm (using the same model configuration of fixed-effect covariates as in the primary endpoint).

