9. STATISTICAL ANALYSIS

9.1 Primary study parameter(s)

The primary outcome is the proportion at risk of HCV infection (as determined by a HCV-MOSAIC score ≥ 2.0) during the run-in versus intervention periods. The score is calculated by summing up the beta-coefficients specific to six self-reported risk factors when present in the previous 6 months (see [Chapter 7.1.1](#)). The HCV-MOSAIC risk score has been previously validated for acute (primary) HCV-infection in HIV-positive MSM and the optimal cut-off to predict HCV positivity was defined at ≥ 2.0 .(65) In addition, we recently evaluated whether the risk score could also identify individuals at high-risk of HCV reinfection, showing comparable performance (The Area Under the ROC Curve = 0.76) to that of primary acute HCV-infection.(66)

The six items of the HCV-MOSAIC risk score will be obtained using the answers from the study questionnaire every six months. The proportion achieving the primary outcome will be summarized at month 6, 12, 18 and 24 visits within each study arm. The probability of the primary outcome will be compared between the run-in (month 6) and intervention periods (month 12, month 18, month 24) using a mixed-effect logistic regression model. In this model, each individual will serve as their own control and between-individual differences at baseline will be accounted for using a random-intercept. Pre versus post-intervention odds ratios (ORs) and their 95% confidence intervals (CI) will be estimated and stratified on study arm, allowing us to identify interventions with significant differences. No multivariable adjustments will be applied. Additional analysis will be conducted in which ORs between arms will be compared by including and testing an interaction term between period and arm in the model (two arms at a time, for a possible three comparisons). No *p*-value adjustments will be made for multiple comparisons to avoid unnecessary correction on the possibly underpowered test for interaction.(67)

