Analyses will be performed by intention to treat (ITT) and per protocol (PP). Both analyses will only include individuals completing the lead-in phase (month-6). ITT analysis is defined by including all observations, while assuming that any individual lost to follow-up did not achieve the primary endpoint. PP analysis is defined by including all available observations, while excluding observations after an individual has been lost to follow-up. Subgroup analysis will also be conducted in order to determine whether individuals with certain characteristics are more likely to have a decrease in HCV-MOSAIC score.

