1.4. SAMPLE SIZE

We aim to have a minimum of 78 individuals per arm (total of 234) who complete at least one study questionnaire during the intervention period. Assuming a maximum drop-out rate of 5% during the run-in period, 246 participants in total are needed to be enrolled. We simulated power under varying proportions at risk of HCV infection during the run-in period and absolute risk reduction during the intervention. With a sample size of 78 in each arm, we would have 80% power to demonstrate a statistically significant difference, at a type 1 error of 0.05, of a >22% reduction in the primary endpoint from a 60% proportion at risk of HCV infection during the run-in period.

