2.1.1. Primary endpoints

- **Definition**

The primary endpoint is the proportion at risk of HCV infection, as determined by the previously developed and validated HCV-MOSAIC risk score [1], which is compared between the run-in and intervention periods, within each arm.

- **Strategy for the main analysis**

Analyses are performed:

- By intent-to-treat (ITT): including all observations and analysed according to the intervention to which the participants were originally assigned, regardless of which intervention they received. This analysis assumes that any individual who was lost to follow-up did not achieve the primary endpoint (i.e., are at risk of HCV infection). Participants who are mistakenly included due to major eligibility criterion(a) not being met are removed from the analysis.
- By per protocol (PP): including all available observations and analysed according to the intervention to which the participants were originally assigned. This analysis excludes all observations after an individual has been lost to follow-up. Participants who are mistakenly included due to major eligibility criterion(a) not being met are removed from the analysis as well as participants who did not receive the intervention to which they were originally assigned.

- **Sensitivity analysis**

The following sensitivity analyses will be performed;

- Including only MSM who used the assigned intervention(s) (both ITT and PP).
- Including only MSM who were at risk of HCV infection at randomization, as determined by the HCV-MOSAIC score (both ITT and PP).
- Correction for issues in adherence and differential loss to follow-up (only PP): identifying pre-randomisation and post-randomisation covariates that predict adherence to the intervention. Depending on the mechanism of inadequate adherence and loss to follow-up, adjustment for confounding by adherence, g-methods or both will be entertained [2].

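### The protocol and SAP define the primary within-arm test in different ways, name no deciding result, and tie the stated 80% power to none of the planned tests

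*SAP*

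**What the plan says.** **Protocol 9.1.** The probability of being at risk (HCV-MOSAIC score of 2.0 or more) is "compared between the run-in (month 6) and intervention periods (month 12, month 18, month 24"), in a random-intercept logistic model giving pre versus post odds ratios by arm. On covariates: "No multivariable adjustments will be applied". On populations: "Analyses will be performed by intention to treat (ITT) and per protocol (PP").

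**SAP 2.2.2.** The endpoint is "compared between the run-in period (i.e., at M0, M6) and at each time point during the intervention period (i.e., at M12, M18, M24"), tested within arm. "Comparisons between run-in and intervention time points are systematically conducted as follows": unadjusted, adjusted for randomisation strata, and adjusted for covariates that might affect the outcome.

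**SAP 2.1.1 and 3.4.1.** The first defines the endpoint as a proportion "which is compared between the run-in and intervention periods, within each arm". The second, headed as the main analysis, has it "compared between the run-in (i.e., M0 to M6) and intervention periods (i.e., M12 to M24"). ITT and PP both appear under the main analysis strategy. In the ITT analysis, men lost to follow-up are counted as at risk.

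**Power (SAP 1.4; protocol 4.4 is equivalent).** With 78 per arm the trial has "80% power to demonstrate a statistically significant difference, at a type 1 error of 0.05, of a >22% reduction in the primary endpoint", starting from 60% at risk. Power is said to have been simulated on an absolute risk reduction scale. Neither section states the visits compared, the within-person correlation, the analysis population or any loss after randomisation. SAP 1.4 defines the 78 as men with at least one intervention-period questionnaire. Enrolment of 246 allows for 5% loss in the run-in.

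**The concern.** Protocol section 3 says the purpose of this pilot is to judge, within each arm, whether a significant decrease can be seen. That needs one test per arm. The documents instead offer two run-in references, visit-level and period-level contrasts, up to three adjustment versions and two populations. SAP 2.2.2 alone yields 3 visits x 3 adjustments x 2 populations = 18 results per arm, unranked. Analysts following different sections could report opposite conclusions for the same arm, and each could cite the plan.

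The power statement has the same gap. A reader cannot tell which test it supports, or whether it allows for the ITT rule, which pulls the observed effect towards zero as men are lost.

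**Working it through.** **1. The definitions side by side**

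| Section | Run-in reference | Intervention side | Adjustment |
|---|---|---|---|
| Protocol 9.1 | M6 | period (M12, M18, M24) | none |
| SAP 2.2.2 | M0 and M6 | each of M12, M18, M24 | three versions |
| SAP 2.1.1, 3.4.1 | run-in period (M0 to M6 in 3.4.1) | period (M12 to M24 in 3.4.1) | not stated |

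All are run in ITT and PP, with neither named as primary.

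**2. Reproducing the stated 80%**

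Inputs from SAP 1.4 and protocol 4.4: n = 78, 60% falling to 38% (absolute), alpha 0.05. Two-sided testing is assumed, because sidedness is not given. Treat the two proportions as independent:

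- SE = sqrt[(0.60 x 0.40 + 0.38 x 0.62)/78] = sqrt(0.4756/78) = 0.0781.
- Unpooled: 0.22/0.0781 - 1.96 = 0.857, power 80.4%.
- Pooled null variance: (0.22 - 1.96 x sqrt(2 x 0.49 x 0.51/78))/0.0781 = 0.808, power 79.0%.

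So the figure is sound arithmetic for two independent groups at one visit. The planned tests are all within-person, with several visits.

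**3. The planned contrasts with complete data**

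For a mean of *a* run-in visits against a mean of *b* intervention visits with common correlation r, the per-man variance is

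V = v1[1+(a-1)r]/a + v2[1+(b-1)r]/b - 2r sqrt(v1 v2), with v1 = 0.24 and v2 = 0.2356.

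At an assumed r = 0.3:

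- M6 versus pooled M12-M24: V = 0.24 + 0.1257 - 0.1427 = 0.2230; power = Phi(0.22/sqrt(0.2230/78) - 1.96) = 98.4%.
- M0+M6 versus one visit: V = 0.156 + 0.2356 - 0.1427 = 0.2489; power 97.3%.
- M0+M6 versus pooled: V = 0.156 + 0.1257 - 0.1427 = 0.1390; power 99.9%.

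Simulation from a random-intercept logit model (SD 1.5 and 2.5, correlation 0.29 and 0.47) agrees: about 96% or more for every planned contrast.

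**4. Effect of the lost-equals-at-risk rule**

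- 10% loss: 0.60 - (0.90 x 0.38 + 0.10) = 0.158.
- 20% loss: 0.60 - (0.80 x 0.38 + 0.20) = 0.096.

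Simulated power for a true 22-point fall is below. Each range covers both correlations and two analyses: a within-person t-test (8,000 runs) and a mixed logistic Wald test (400 runs). Loss rates are assumed.

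| Test | 5/10/15% lost by M12/M18/M24 (average 10%) | 10/20/30% (average 20%) |
|---|---|---|
| ITT, period vs M6 | 76-91% | 35-47% |
| ITT, period vs M0+M6 | 91-98% | 48-64% |
| PP, period vs M6 | about 97% or more | 95% or more |

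At 10% average loss the ITT visit tests against M0+M6 give M12 88-94%, M18 73-86% and M24 53-68%.

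**5. How often the readings disagree on significance**

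The first row changes the reference alone and uses the t-test only. The others cover both analyses under loss.

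| Pair | No loss, 22-point fall | 10% average loss, 22-point fall |
|---|---|---|
| Period vs M6, against period vs M0+M6 (ITT) | 0.5-2% | 11-17% |
| Protocol test against SAP M24 test (ITT) | 1-4% | 27-32% |
| ITT against PP (period vs M6) | 0% | 9-21% |

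With no loss but a 15-point true fall, the reference conflict alone changes the answer in about 11-17% of trials. The three adjustment versions were not simulated.

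**6. Enrolment**

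246 x 0.95 = 233.7, about 3 x 78 = 234. This covers run-in loss only, although SAP 1.4 counts men who have also returned a later questionnaire. Protocol 7.5 allows withdrawals to be replaced while recruitment is open.

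**The case against.** **The SAP governs.** It calls itself a more detailed description of the protocol's analysis. It does not say that it replaces protocol 9.1, and that would still leave SAP 2.2.2 against 3.4.1.

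**Protocol 9.1 could be read visit by visit.** It writes of intervention periods in the plural and summarises by visit. Its single pre/post odds ratio and its period-by-arm term favour pooling, but the wording is not decisive. The reference and adjustment conflicts do not depend on this, and the visit-versus-period conflict is clearest inside the SAP.

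**It is a pilot.** True, and this limits the harm to an unclear conclusion per arm. It does not remove the need for a deciding test.

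**The loss rates are assumed.** This stands. The only documented rate is a maximum of 5% over the run-in. If all 78 return M12, as SAP 1.4 defines them, and 5% and 10% are then lost by M18 and M24, ITT power for period versus M6 is 92-97% by t-test.

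**M0.** A reader might infer that M0 contradicts the SAP's own run-in, because SAP 2.3.1 starts run-in follow-up at inclusion while the M0 questionnaire looks back 6 months. The documents do not support this. SAP 2.3.1 defines follow-up time, and SAP 2.1.2, 2.2.2 and 3.4.1 all assign M0 to the run-in. That M0 recall precedes enrolment bears on interpretation and is not an inconsistency.

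**Conclusion.** The conflict is real and can be read directly from the current texts: reference, contrast and adjustment differ, ITT and PP are unranked, and no result is named as deciding. This conclusion needs no assumption.

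The power figure is unassigned rather than wrong. It fits an independent-groups comparison that is not planned. It is conservative for the planned tests with little loss or in PP, roughly right for ITT period versus M6 at about 10% average loss, and optimistic above that. Those statements rest on the assumed correlations (0.29-0.47), the assumed loss patterns and a constant 22-point effect.

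Two stronger readings should be resisted. One is that the trial is underpowered: with complete data every planned contrast exceeds 80%, and any shortfall depends on loss rates that the documents do not give. The other is that the wording conflict by itself produces the high disagreement rates: most of the 27-32% comes from assumed loss under the ITT rule. At the design effect with no loss, the reference conflict alone changes the answer in only 0.5-2% of trials, though this rises to 11-17% if the true fall is 15 points.

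The change should be made before analysis.

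**What to change.** In protocol 9.1 and SAP 2.2.2 and 3.4.1, name the same single primary test for each arm:

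- one run-in reference, either M6 or M0+M6; if M0 is kept, note that its 6-month recall precedes enrolment;
- one contrast (pooled M12-M24 would match SAP 2.1.1 and 3.4.1);
- one adjustment version (unadjusted would match protocol 9.1);
- one analysis population.

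Label all other visit, adjusted and population results supportive, and state that the three arm tests are not adjusted for multiplicity.

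In SAP 1.4 and protocol 4.4, restate the power or the detectable difference for that test. Give the assumed within-person correlation and, if ITT is chosen, the assumed loss after randomisation under the lost-equals-at-risk rule.

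The cost is wording and one re-run of the power simulation. No planned result is dropped, and no extra participants are needed unless the sponsor chooses to cover loss after randomisation.
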